**Last updated: 2.1.2019**

## Project summary

Increased health education has the potential to facilitate better use of health care services and to promote early treatment, thus it can strengthen the health care system, and ultimately reduce morbidity and mortality. In this study, we will develop and test the effect of digital health messages related to HIV, Tuberculosis (TB) and *Taenia solium* cysticercosis/taeniosis (TSCT) (the intervention diseases) in Migoli and Izazi (the intervention villages), in Iringa, Tanzania (TZ).

The intervention is planned as follows: A digital platform, providing the intervention villages with digital health messages related to the above-mentioned diseases, will be implemented in TZ in 2019. The platform will be accessible free of charge, through own devices and tablets based in the local Wi-Fi spots in the villages.

In the first part of the PhD-project, the doctoral research fellow will participate in developing the digital health messages, together with experts from the medical and teaching environments in Tanzania, Norway, Germany and USA.

The second part of the PhD-project consists of a cluster non-randomised controlled trial and semi-structured interviews in Tanzania. The digital health messages will be physically shown to the participants in the intervention group. The study is planned to investigate the knowledge related to the intervention diseases, before the intervention, immediately after exposure to the intervention, and at follow-up points throughout one year, after the intervention has been implemented. Semi-structured interviews with clients (users of the intervention) from each of the intervention villages are included, to explore the perception and reception of the intervention.

The baseline study and the immediate after survey will take place in Tanzania in Q1 2019, while the other follow-up studies and interviews (3, 6 and 12 months after baseline) will be undertaken throughout one year.

## Introduction

This protocol is registered in Helseforsk, University of Oslo, and the project has been assessed by Norwegian Centre for Research Data (NSD), ref. number 59643. Ethical approval from the National Institute for Medical Research (NIMR), Tanzania, has been granted with the reference number NIMR/HQ/R.8a/Vol IX/2947.

The PhD-project consist of three work packages: WP1: A systematic review and meta-analysis, WP2: A cluster non-randomised controlled trial and WP3: Semi-structured interviews with clients in the intervention group. Only WP2 and WP3 are elaborated upon in this protocol.

The planned PhD-project will be included as a health-research component in the Norwegian Government- and Norwegian Research Council- funded innovation project "*Non-discriminating access for Digital Inclusion*" (DigI). The project runs from January 2017 to September 2020. Altogether 11 partnersi from eight countries are collaborating on the project. [name] from the Dept. of Technology Systems (ITS), University of Oslo (UiO), is the project owner, and the doctoral research fellow's co-supervisor. Responsible for the health-research component and main supervisor of the doctoral research fellow, is [name]. [name] at the Institute of Health and Society, UiO. Head in TZ, is [name] (HIV/AIDS and TB specialist) from NIMR and Associate professor [name] (TSCT specialist) from Sokoine University of Agriculture (SUA). Associate professor [name] from Dept. of Information and Communication Technology at University of Agder is head of developing the digital health messages. This study is thus multicentre with several institutions responsible for research.

In Tanzania, DigI will facilitate a digital health education platform, where digital health messages related to HIV / AIDS, Tuberculosis (TB) and *Taenia solium* cysticercosis/taeniosis (TSCT) will be transferred to the community; hereby called clients, defined by the World Health Organization (2017) as "*members of the public that are potential or current users of health services, including promotion activities*".

---

i The partners are: Basic Internet Foundation, The University of Oslo, Orange, Ministry of Health (TZ), National Institute for Medical Research (TZ), Sokoine University of Agriculture (TZ), Mondragon University (Spain), Global Health Media Project (US), IPX Extenso, Future Competence and Motivation

The digital health messages will be accessible at a Wi-Fi spot in the local village close to the local health post. The digital health messages will also be shown face-to-face to each of the participants in the intervention group, by enumerators in the research team from SUA and the doctoral research fellow. The intervention will be available for all clients in the intervention villages, not only for the participants in the study described in this protocol.

The intervention will be maintained by NIMR Muhimbili Centre in Dar es Salaam during the first phase, but is going to be managed as a sustainable business model where a local sales man or woman is selling vouchers to access the World Wide Web. NIMR have close contact with the village authorities and health workers in the intervention villages, and will be alerted if the intervention for some reason is not functioning. The Wi-Fi network that provides the access to the digital health education platform, reaches within a radius of 50 meters, and is driven by a solar panel. This means that the intervention will be accessible even if the electricity locally shuts down.

## Background and Rationale

Today's education channels are changing, thus health education interventions must meet the target population at their own level of technology, and further do rely upon the characteristics of the technology available. A useful tool to deliver education and improve health seeking behaviour and health-related lifestyle decisions, is mobile technologies, because they make people more contactable. Health seeking behaviour may change after the target group has been exposed to adequate health messages that provide relevant information to the target population, thus digital health information can contribute to prevention and management of diseases.

### Digital health and digital health education

Digital health is defined by WHO (2016) as *"The use of digital, mobile and wireless technologies to support the achievement of health objectives. Digital health describes the general use of information and communications technologies (ICT) for health and is inclusive of both mHealth and eHealth"*. eHealth is defined by the WHO (2005) as *"the cost-effective and secure use of information and communications technologies in support of health and health-related fields, including health-care services, health surveillance, health literature, and health education, knowledge and research"*. mHealth is a component of eHealth, and commonly referred to as the use of mobile and wireless technologies for health. WHO (2011) defines it as: *"medical and public health practice supported by mobile devices, such as mobile phones, patient monitoring devices, personal digital assistants (PDAs), and other wireless devices"*.

Health behaviour change may reduce the burden of preventable disease and death around the world, *"as health education covers the continuum from disease prevention and promotion of optimal health to the detection of illness to treatment, rehabilitation, and long-term care"*.

The use of eHealth is now understood as central in order to provide more care and better care to more people, especially those most in need. A key part of the Sustainable Development Goal 3 relates to reaching people with the information they need in order to live healthier lives, and eHealth is regarded as a tool to reach the public with health messages and support, as well as encouraging clients to take active roles in their health and wellbeing (ibid).

The use of smart devices and mobile data services are rapidly changing, and it is likely that an increasingly part of the population in for example Sub-Saharan Africa will have access to both in the future.

### Focus diseases

Creating awareness of prevalence, causes / transmission, symptoms, how to treat and prevention of diseases, aiming to provide early treatment and increase appropriate use of health care services in rural areas in the global south, is important in order to reducing infectious diseases like HIV/AIDS, TB and zoonotic diseases like TSCT. In lower income countries (World Bank classification) 60% of the population live in rural areas. These are hard to access populations, due to underdeveloped infrastructure and resource poverty, which need the

health education already available.

Related to this project, the spread of information regarding the following diseases will be essential:

### **HIV/AIDS**

In sub-Saharan Africa, AIDS is the leading cause of death among teenagers, and 25.6 million people in Africa are living with HIV in 2016. Quality information, rapid diagnosis and early treatment and care are essential to control the virus and help prevent transmission to others.

### **Tuberculosis (TB)**

TB treatment saved 49 million lives globally between 2000 and 2015, but despite TB being both treatable and curable, 1.7 million people are dying globally from the disease, each year. The most efficient way to save lives is to diagnose and treat TB as early as possible.

### ***Taenia solium* (neuro)cysticercosis/taeniosis (TSCT)**

TSCT is an emerging but neglected parasitic and zoonotic disease, caused by the tapeworm *Taenia solium*. In humans the disease manifests itself mainly as neurocysticercosis (NCC) - the most frequent preventable cause of epilepsy in sub-Saharan Africa. TSCT has been listed as a priority disease for international attention towards elimination, to alleviate poverty.

Messages on Anthrax, Cholera and maternal and new born health will also be available, but they are not part of this particular PhD-project.

## **Objectives**

The overarching objective of the study is to acquire new knowledge within the field of digital health education / digital health promotion and health literacy of clients in Iringa, Tanzania. The study will employ both quantitative and qualitative methods (mixed method) of data collection and analysis. The primary objective of the PhD-project is to develop, describe and understand the use of a digital health literacy intervention, and its effect on health literacy outcomes in Migoli and Izazi, Iringa, Tanzania.

### **Main objectives in WP 2**

- Assess the effect of the digital health intervention, related to knowledge uptake and knowledge retention by assessing the knowledge score before and after the intervention, in both groups.
- To investigate if the intervention increase health literacy related to the intervention diseases among the clients that cannot read.

### **Main objectives in WP 3**

- Explore the reception and perception of the intervention among the users, by semi-structured interviews.

The doctoral research fellow will strive to present and review the findings from the research within the Sustainable Development Goals (SDGs), as over-arching framework. There are especially two goals of major importance related to this study: SDG 3 *Good health and well-being*, and SDG 9 *Industry, innovation and infrastructure*.

One of the targets in SDG 3, states that they are making a bold commitment to end the epidemics of (among others) HIV/AIDS and TB by 2030. Another target emphasizes to strengthen the capacity of all countries, in particular developing countries, for early warning, risk reduction and management of national and global health risks. Bridging the digital gap is an important task related to targets of SDG 9. They state among other targets: “*Significantly increase access to information and communications technology and strive to provide universal and affordable access to the Internet in least developed countries by 2020*”. The DigI project directly addresses this target through the aim of free access to information for all. The free access to information is also the catalyst for several other SDG goals (4, 8, 10 and 11).

## **WP 2 –A cluster non-randomised controlled trial**

The overall strategy chosen is a non-randomised controlled trial, with a two-stage cluster sampling. The study will be conducted in four villages in Iringa district in Tanzania, assessing the effect of digital health messages related to HIV / AIDS, Tuberculosis (TB) and *Taenia solium* cysticercosis/taeniosis (TSCT).

The aim of the digital health intervention is to contribute to increased health knowledge of the clients that has the potential to facilitate better use of health care services, and to promote early treatment, thus to strengthen the health system.

Hypotheses: We hypothesize that the intervention increases the proportion of correct answers, related to the intervention diseases, when comparing pre and post knowledge scores, also among clients that cannot read.

We will measure if the intervention leads to an increase in the number of correctly answered questions, from 21 out of 42, to 28 out of 42 (equivalent to 16,7 % increase) questions from the study questionnaire, during the 12-months intervention in the intervention group compared to the control group.

### **Methods and study design**

Iringa district was selected because the prevalence of all three diseases is high, and the areas are known to be endemic, in addition to being a rural district with mainly unconnected villages. The intervention villages were conveniently chosen at an early stage in the DigI project, thus randomization of the participants to intervention / control groups will not be feasible. The intervention group, group 1, consists of randomly selected participants from the villages Izazi and Migoli.

Izazi village is not connected to internet, while Migoli has recently been connected through 3G. According to the village authorities, 3G is not used for health information.

The control group, group 2, consists of randomly selected participants from the villages Kimande and Idodi. These villages are candidates for the 7 next villages to get access to the digital health platform, in the DigI project phase II. The control villages are both located at least 70 km away from the intervention villages, and have at least three villages in between, in order to hinder contamination between the two groups.

Around 494 participants (15-70 years of age) will be included in the study. The study will take place at randomly selected households in the four villages. The ten-cells (sub-villages with up to 50 households) will be the clusters and randomization will occur at ten-cell and household level. Group 1 will receive a 12- months intervention, and group 2 will function as a control group and will get usual information through the village health posts available resources (see the section on control group below). Study variables will be measured at baseline, immediately after exposure to the intervention, 3, 6 and 12 months after exposure. The main outcome will be knowledge uptake and score after intervention, and scores related to retention of knowledge throughout the year.

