### **Recruitment and participants**

The research population is people living in the selected villages, the study units are individuals, but only people over 15-70 years old are eligible for participating in the study. This is a two-stage cluster where the intervention villages initially were sampled by stratification, and two-stage sampling frame will be undertaken at a ten-cell and household level. The number of households within the ten-cells will be selected by the size of the ten-cell, according to the Probability Proportional to Size. In the randomly chosen households, 3-4 household members will be interviewed all together five times. Ten-cell and household lists will be used for randomisation in both groups.

A baseline survey conducted in both groups will determine the knowledge with regard to the diseases in the groups before the intervention is implemented.

In group 1, the random selected sample of people, previously naïve to health messages delivered by the DigiI project, will be given the intervention physically, as they will be shown the digital health messages at the researchers/ enumerators tablets. This is to make sure that all the participants in group 1 will actually receive the intervention, in order for the analysis to be able to indicate the overall effect of the digital health messages. All the participants in group 1 will be informed that the intervention is available for all, at all times, in the local Wi-Fi spot, however, we cannot be certain that the participants will use the intervention more than the first exposure by the enumerators.

Group 1 will, immediately after the exposure to the digital health messages, be asked the same questions as in the baseline questionnaire. 3 months, 6 months and 12 months after first exposure to the intervention, the questions will be repeated to the same participants.

Inclusion criteria:

- Living in the selected household (15-70 years), at least for the past six months, and at least planning to not move the next 12 months.
- Must be capable and willing to sign written informed consent and thumb-print for illiterate participants

Exclusion criteria

- Planning to be out of the village for more than 6 weeks in the next 12 months
- Those above 71 or under 15
- Not capable of signing consent letter (very sick)

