**Sample size calculation**

The data will be gathered from Migoli village, Mtera ward and Izazi Village, in Izazi ward (both in Iringa, population 10.036 and 2.567 people), in addition to the control villages, Kimande village in Pawaga ward and Idodi village in Idodi ward, also in Iringa district. After internal discussion in the DigI group, it is assumed that the people would have 21 correct answers out of 42 questions in total, if they were

Sample size per village			
	Population	Proportion	Sample
Migoli	10036	0,79	195
Control village 1, Kimande	3000	0,55	135
Izazi	2657	0,21	52
Control village 2, Idodi	2500	0,45	112
N	18193		
Sample			494

Table 2

asked questions from the questionnaire today. It is further assumed that the intervention will increase the number of correct answers to at least 28 of 42. The sample size calculation is to be found in appendix 1. The power of the study was set to 80%, the drop-outs calculated to be 20% and the cluster correlation was set to 1,5. After calculating the sample size, the proportions to each village was allocated, see table 2.

After ethical approval from NIMR is granted, the questionnaire will be piloted in a village near Morogoro to see how it corresponds with the assumed proportion mentioned (at least 21 correct answers out of 42).

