**Data management and statistical analysis**

A data management plan is being developed using a tool from the Norwegian Centre for Research Data (NSD). UiO is responsible for the data stored in TSD. The de-identification code will be stored separately in TSD, and deleted in 2022. After this, the anonymous data will be kept in NSDs archives, for re-use purposes.

The data will be analysed in TSD, by multilevel models to address the dependency related to cluster trials. Summary tables with calculated averages (mean, median, and mode), will be created. The baseline knowledge scores will be calculated with data from the first survey. The doctoral research fellow will compute an overall score for each section (prevalence, cause/transmission, symptoms, treatment and prevention) at individual and village level, based on the answers to the questions. Then a comparison between intervention groups and between intervention and control groups will be made. Data from the follow-ups will also be analysed in TSD accordingly.

After data collection is completed the GPS data will be able to illustrate the use of the intervention, related to distance from household to Wi-Fi spot and frequency of use. In this planned illustration, no direct households will be identified, but rather summarize on village level the frequency of the use of the intervention.

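### Group is assigned by village, two against two, but the ten-cells are named as the clusters, and nothing in the supplied text allows for villages changing differently over time

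*Combined protocol and SAP*

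**What the plan says.** Methods and study design (WP 2) puts Izazi and Migoli in the intervention group and Kimande and Idodi in the control group. It is open about how this came about: "The intervention villages were conveniently chosen at an early stage", so that "randomization of the participants to intervention / control groups will not be feasible". Of the control villages it says: "These villages are candidates for the 7 next villages to get access to the digital health platform". The same section then defines the clusters: "The ten-cells (sub-villages with up to 50 households) will be the clusters and randomization will occur at ten-cell and household level". Recruitment and participants makes clear that this second kind of randomisation is sampling: "two-stage sampling frame will be undertaken at a ten-cell and household level".

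Sample size calculation states: "The power of the study was set to 80%, the drop-outs calculated to be 20% and the cluster correlation was set to 1,5". It refers to Appendix 1 for the calculation and continues: "After calculating the sample size, the proportions to each village was allocated, see table 2". Table 2 gives Migoli 195 and Izazi 52 (247 together), and Kimande 135 and Idodi 112 (247 together).

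Data management and statistical analysis plans to analyse the data "by multilevel models to address the dependency related to cluster trials". No levels, role for village or method for few clusters are given. It does plan knowledge scores at individual and at village level.

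**The concern.** Everyone in a village is in the same group, so the village is the unit of assignment and there are two per group. Ten-cells are sampled inside villages; no ten-cell could have gone to the other group. An analyst who follows the cluster definition as written would fit ten-cells as the only clustering level and treat them as independent evidence on the group difference.

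Measuring both groups before and after removes stable differences between villages. It does not remove differences in how villages change over the year, for example through local health activity or new connectivity. If such differences exist and village is left out, the standard error of the group comparison is too small. At stake are the between-group comparisons at 3, 6 and 12 months and the meaning of the 80%. The immediate-after questionnaire is given only in the intervention group (Recruitment and participants; Study tools), so it is not a between-group comparison and is outside this point.

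**Working it through.** **1. The plan's own figure.** Inputs: 21/42 = 0.500 and 28/42 = 0.667, power 80%, drop-out 20%, factor 1.5. Two-sided 5% is assumed, because the supplied text does not state it.

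n per group = [1.96·√(2·0.5833·0.4167) + 0.8416·√(0.25 + 0.2222)]² / 0.1667² = 136.17, rounded up to 137.

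137 × 1.5 × 1.2 = 246.6, rounded up to 247; two groups give 494, as in Table 2.

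A second route (0.667 rounded to 0.67, n = 131, times 1.5, divided by 0.8, rounding up at each step) also gives 494. Both use one factor of 1.5 and no other inflation. The plan calls it a correlation, but a correlation cannot exceed 1. It acts as a design effect.

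**2. What the 1.5 can cover.** Design effect = 1 + (m − 1)·ICC.

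- As a ten-cell factor, with 10 people per ten-cell (assumed; the plan gives no number): ICC = 0.5/9 = 0.056. Nothing is left for villages.
- As a village factor, the effective village size is Σn²/Σn. Intervention: (195² + 52²)/247 = 164.9. Control: (135² + 112²)/247 = 124.6. The mean is 144.7, or 115.8 after 20% loss. ICC = 0.5/143.7 = 0.0035, or 0.5/114.8 = 0.0044. Nothing is left for ten-cells or households.

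**3. Type I error if village variation in change is left out.** All SDs are assumptions, in items out of 42. With 0.8 × 247 = 197.6 people per group analysed:

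- Variance the model sees: V0 = 2 × 1.5 × SD²/197.6.
- True variance: V1 = V0 + SDv² × [(195² + 52²)/247² + (135² + 112²)/247²] = V0 + 1.172·SDv².
- Type I error = 2·[1 − Φ(1.96·√(V0/V1))].

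For a village SD of change (SDv) of 1 item:

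| Person SD | V0 | V1 | Type I error | Village ICC |
|---|---|---|---|---|
| 5 | 0.380 | 1.551 | 33% | 0.038 |
| 7 | 0.744 | 1.916 | 22% | 0.020 |
| 9 | 1.230 | 2.402 | 16% | 0.012 |
| 20.7 (yes/no scale) | 6.51 | 7.68 | 7% | – |

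The last row is the scale of the sample-size formula, which treats each person as one yes/no result: 42 × √(0.5833 × 0.4167) = 20.7 items.

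A simulation agrees (6000 runs, change scores, about 10 people per ten-cell, ten-cell ICC 0.05, 20% loss). A test on ten-cell means rejected a true null in 33%, 22% and 17% of runs at person SD 5, 7 and 9 with a village SD of 1. At a village SD of 0.5 it rejected in 15%, 10% and 8%, and at 0 in about 5%. A t test on village means stayed at 4–5%.

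**4. Power of a village-level comparison.** Difference in equally weighted village mean changes, t on 4 − 2 = 2 df (critical value 4.303), Var = Σ[SDv² + 1.5·SD²/(0.8n)]/4 over the four villages, true difference 7 items:

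| Village SD | Power, person SD 9 to 5 | 95% half-width, person SD 5 to 9 |
|---|---|---|
| 0 | 80–99% | 3.0–5.3 items |
| 1 | 63–81% | 5.2–6.9 items |
| 2 | 38–44% | 9.1–10.1 items |

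**The case against.** Several counter-arguments carry weight.

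- Appendix 1 is not in the supplied text and may say which level the 1.5 refers to. That stands: the point is that no allowance can be identified in what is available. The arithmetic does show that there is only one factor.
- Nothing in the analysis section rules out a village level, and village-level scores are already planned. Also true; the inflated error rates describe the ten-cell reading, not a demonstrated fault of the final analysis. But village-level scores are summaries, and the only cluster definition given names the ten-cells.
- The size depends heavily on scale: 7% on the formula's yes/no scale against 16–33% on the score. This stands, and is why both are shown. The score is the more natural scale, since the outcome is a count of correct answers.
- The plan does not hide that it is non-randomised. A reader might infer from the cluster definition that ten-cells are claimed to be randomised to groups. The neighbouring text and the sampling section contradict that, so the repair there is mainly one of wording.

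A reader might also infer that the trial is underpowered. The documents do not support this: they give no SD or ICC, and under the assumed values the 2-df power lies on either side of 80%. Nor would it be right to say that clustering was ignored, because a factor of 1.5 was applied.

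**Conclusion.** The concern holds as a mismatch between the unit of assignment and the stated clusters, with an analysis that does not resolve it. The 80% is conditional on the four villages having the same time trend, and the plan does not say so. If they do not and only ten-cells are modelled, the 3-, 6- and 12-month comparisons are anti-conservative, by an amount that cannot be fixed from the documents. Reduced power is not demonstrated.

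The conclusion rests on a two-sided 5% level, on reading the 1.5 as a design effect, and on Appendix 1 containing no further allowance. The existence of the gap does not depend on the assumed SDs; only the illustrated sizes do. Because the villages were neither randomly chosen nor randomly assigned, neither a ten-cell model nor a village-level test supports a claim beyond these four villages. It should be fixed, but does not call the study itself into question.

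**What to change.** - **Methods and study design:** state that the village is the unit of assignment, two per group, and that ten-cells and households are sampled at random within villages and are not randomised to groups.
- **Sample size calculation:** call the 1.5 a design effect, state which level it refers to, and say that the 80% is conditional on these four villages with no village-by-time variation.
- **Data management and statistical analysis:** name the levels (village, ten-cell, household, person, time) and how village enters the model. Extend the planned village-level scores to show each village's change from baseline. Add a sensitivity analysis of the difference in village mean change with t on 2 df. Limit conclusions to these four villages.

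The cost is wording in three sections and one extra analysis, with no added participants, villages or visits. The downside is real: the stated power and the strength of the conclusion become less favourable, and the 2-df interval may be inconclusive.
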